9. TRIAL DOCUMENTATION, MONITORING, AND ADMINISTRATION

9.1 TRIAL DOCUMENTATION

The investigator must maintain adequate and accurate records to enable the conduct of the trial to be fully documented, including, but not limited to, the protocol, protocol amendments, Informed Consent Forms, and documentation of IRB/EC and governmental approval. In addition, at the end of the trial, the investigator will receive the patient data, including an audit trail containing a complete record of all changes to the data.

9.2 PROTOCOL DEVIATIONS

The investigator should document and explain any protocol deviations. The investigator should promptly report any deviations that might have an impact on patient safety and data integrity to the Sponsor and to the IRB/EC in accordance with established IRB/EC policies and procedures.

9.3 SITE INSPECTIONS

Site visits will be conducted by the Sponsor or an authorized representative for inspection of trial data, patients' medical records, and eCRFs. The investigator will permit national and local health authorities; Sponsor monitors, representatives, and collaborators; and the IRBs/ECs to inspect facilities and records relevant to this trial.

9.4 ADMINISTRATIVE STRUCTURE

An iDMC will review safety data and advise on trial conduct (see Section 3.1). The procedures that will be used by the iDMC will be detailed in an iDMC charter. The IxRS system will be used to conduct the randomization process (see Section 4.2) and to confirm the shipment condition and content of the IMPs (see Section 4.3.3). A CRO will be responsible for data management of this trial (see Section 7.1).

9.5 PUBLICATION OF DATA AND PROTECTION OF TRADE SECRETS

Regardless of the outcome of a trial, the Sponsor is dedicated to openly providing information on the trial to healthcare professionals and to the public, both at scientific congresses and in peer-reviewed journals. The Sponsor will comply with all requirements for publication of trial results. For more information, refer to the Roche Global Policy on Sharing of Clinical Study Information at the following Web site:

http://www.roche.com/dam/jcr:1c46aa73-cea0-4b9b-8eaa-e9a788ed021b/en/roche_global_policy_on_sharing_of_clinical_study_information.pdf

The results of this trial may be published or presented at scientific congresses. For all clinical trials in patients involving an IMP for which a marketing authorization application has been filed or approved in any country, the Sponsor aims to submit a journal manuscript reporting primary clinical trial results within 6 months after the availability of the respective Clinical Study Report. In addition, for all clinical trials in patients involving an IMP for which a marketing authorization application has been filed or approved in any country, the Sponsor aims to publish results from analyses of additional endpoints and exploratory data that are clinically meaningful and statistically sound.

The investigator must agree to submit all manuscripts or abstracts to the Sponsor prior to submission for publication or presentation. This allows the Sponsor to protect proprietary information and to provide comments based on information from other studies that may not yet be available to the investigator.

In accordance with standard editorial and ethical practice, the Sponsor will generally support publication of multicenter trials only in their entirety and not as individual center data. In this case, a coordinating investigator will be designated by mutual agreement.

Authorship will be determined by mutual agreement and in line with International Committee of Medical Journal Editors authorship requirements. Any formal publication of

the trial in which contribution of Sponsor personnel exceeded that of conventional monitoring will be considered as a joint publication by the investigator and the appropriate Sponsor personnel.

Any inventions and resulting patents, improvements, and/or know-how originating from the use of data from this trial will become and remain the exclusive and unburdened property of the Sponsor, except where agreed otherwise.

9.6 PROTOCOL AMENDMENTS

Any protocol amendments will be prepared by the Sponsor. Protocol amendments will be submitted to the IRB/EC and to regulatory authorities in accordance with local regulatory requirements.

Approval must be obtained from the IRB/EC and regulatory authorities (as locally required) before implementation of any changes, except for changes necessary to eliminate an immediate hazard to patients or changes that involve logistical or administrative aspects only (e.g., change in Medical Monitor or contact information).

Appendix 1 Schedule of Assessments

	Washout ^a	Screening	Double-blind treatment							Early treatment discontinuation ^b	Follow-up ^u	Additional safety follow-up ^c	Additional safety follow-up final visit
Day Week	-50 to -22	-21 to -1	Randomization 1 1	28 4	56 8	84 12	112 16	140 20	168 24		196 28	up to 12 months	up to 12 months plus 28 days
Window (days, unless otherwise stated)				±5	±5	±5	±5	±5	±5	±5 ^b	±5	±5	±5
Treatment Period Visit			1	2	3	4	5	6	7			Month 1 to 6: Monthly visits Month 7 to 12: Approximately every 3 months	
Informed consent ^{d,e}	x	x											
Review Eligibility Criteria		x											
Demographic data ^e	x	x											
General medical history and baseline conditions ^e	x	x											
Vital signs ^f		x	x	x	x	x	x	x	x	x	x	x	
Weight		x							x	x			
Height		x											
Complete physical examination ^g		x	x						x	x			

	Washout ^a	Screening	Double-blind treatment							Early treatment discontinuation ^b	Follow-up ^u	Additional safety follow-up ^c	Additional safety follow-up final visit
Day Week	-50 to -22	-21 to -1	Randomization 1 1	28 4	56 8	84 12	112 16	140 20	168 24		196 28	up to 12 months	up to 12 months plus 28 days
Window (days, unless otherwise stated)				±5	±5	±5	±5	±5	±5	±5 ^b	±5	±5	±5
Treatment Period Visit			1	2	3	4	5	6	7			Month 1 to 6: Monthly visits Month 7 to 12: Approximately every 3 months	
ECG ^h		x	x			x			x	x	x		
Hematology ⁱ		x	x			x			x	x			
Chemistry ^j		x	x	x	x ^k	x	x ^k	x ^k	x	x		x ^k	
Pregnancy test ^l		x	x	x	x	x	x	x	x	x		x	
Trial treatment administration			x	x	x	x	x	x			x ^m	x	
Spirometry (FVC, FEV ₁)		x	x	x	x	x	x	x	x	x			
Daily spirometry (handheld device) ^{n,o}		x	x	x	x	x	x	x	x	x			
DLco		x	x			x			x	x			
6MWD ^p		x	x			x			x	x			
Leicester Cough Questionnaire ^q			x			x			x	x			
UCSD-SOBQ ^q			x			x			x	x			

	Washout ^a	Screening	Double-blind treatment							Early treatment discontinuation ^b	Follow-up ^u	Additional safety follow-up ^c	Additional safety follow-up final visit
Day Week	-50 to -22	-21 to -1	Randomization 1 1	28 4	56 8	84 12	112 16	140 20	168 24		196 28	up to 12 months	up to 12 months plus 28 days
Window (days, unless otherwise stated)				±5	±5	±5	±5	±5	±5	±5 ^b	±5	±5	±5
Treatment Period Visit			1	2	3	4	5	6	7			Month 1 to 6: Monthly visits Month 7 to 12: Approximately every 3 months	
SGRQ ^q			x			x			x	x			
Cough visual analog score ^q			x			x			x	x			
Serum for biomarker assessments			x	x		x			x	x			
Plasma for biomarker assessments			x	x		x			x	x			
Whole blood for PAX gene biomarker assessment			x	x		x			x	x			
Concomitant medications ^r	x	x	x	x	x	x	x	x	x	x	x	x	x
Adverse events ^s		x	x	x	x	x	x	x	x	x	x	x	x
Whole blood sample for RBR (optional) ^t			x										

6MWD=6-minute walk distance; ALT=alanine aminotransferase; AST=aspartate aminotransferase; BUN=blood urea nitrogen; DLco=diffusing capacity of the lung for carbon monoxide; ECG=electrocardiogram; eCRF=electronic case report form; FEV₁=forced expiratory volume in 1 second; FVC=forced vital capacity; IMP=investigational medicinal product; LDH=lactate dehydrogenase; LFT=liver function test; PRO=patient-reported outcome; RBC=red blood cell; RBR=Research Biosample Repository; SGRQ=St. George's Respiratory Questionnaire; SOBQ=Shortness of Breath Questionnaire; UCSD=University of California, San Diego; WBC=white blood cell

Notes: all assessments should be performed within 7 days of the scheduled visit, unless otherwise specified.

- ^a Patients will be required to taper and/or discontinue all prohibited medications in the 28 days prior to the start of screening during the washout period. Patients not taking a prohibited medication will forgo the washout period and directly enter screening.
- ^b Patients who discontinue trial treatment prematurely will return to the site (clinic) for an Early Treatment Discontinuation Visit 28 (± 5) days after the last dose of the double-blind treatment, thus ending their participation in the trial. For patients who end their participation in the double-blind treatment period due to unblinding, they may be offered to continue into the open-label period according to the investigator's judgment. These patients will attend the Early Treatment Discontinuation Visit (28 (± 5) days after the last dose of the double-blind treatment) and on the same day begin their participation in the 12-month open-label pirfenidone safety follow-up period.
- ^c After completion of the double-blind treatment period and the Follow-up Visit at Week 28, the Sponsor will offer the possibility to the patients to receive open-label pirfenidone within the trial protocol in a safety follow-up period of up to 12 months. During the 12-month safety follow-up period, initially, patients will be evaluated at monthly visits for the first 6 months. At the end of the first 6 months, patients will be evaluated at each site visit occurring approximately every 3 months until the end of the safety follow-up period.. A final Follow-up Visit will be performed at the end of the safety period, 28 (± 5) days after the last open-label dose.
- ^d Informed consent must be documented before any trial-specific screening procedure is performed, and may be obtained either at the Washout or Screening Visits.
- ^e Any procedures that were not completed during washout, must be completed at the Screening Visit.
- ^f Includes respiratory rate, pulse rate, and systolic and diastolic blood pressures while the patient is in a seated position, and temperature. Abnormalities observed at baseline should be recorded on the General Medical History and Baseline Conditions eCRF. At subsequent visits, new or worsened clinically significant abnormalities should be recorded on the Adverse Event eCRF. All vital sign measurements are to be obtained prior to any blood draws scheduled at the same time.
- ^g Includes evaluation of the head, eyes, ears, nose, and throat, and the cardiovascular, dermatological, musculoskeletal, respiratory, gastrointestinal, genitourinary, and neurological systems. Abnormalities observed at baseline should be recorded on the General Medical History and Baseline Conditions eCRF. At subsequent visits, new or worsened clinically significant abnormalities should be recorded on the Adverse Event eCRF.
- ^h All ECGs are to be obtained prior to other procedures scheduled at the same time.
- ⁱ Hematology includes WBC count, RBC count, hemoglobin, hematocrit, platelet count, differential count (neutrophils, eosinophils, basophils, monocytes, lymphocytes, other cells).
- ^j Chemistry panel (serum or plasma) includes sodium, potassium, chloride, bicarbonate, glucose, BUN or urea, creatinine, total protein, albumin, phosphorus, calcium, total and direct bilirubin, alkaline phosphatase, ALT, AST, uric acid, LDH.

- ^k Only LFTs (AST, ALT, bilirubin, and alkaline phosphatase) will be conducted at these visits. During the Safety Follow-up period, LFTs will be performed every month during the first 6 months and subsequently at each visit occurring approximately every 3 months thereafter, until the end of this period.
- ^l All women of childbearing potential will have a serum pregnancy test at screening. Urine pregnancy tests will be performed at the specified subsequent visits. If a urine pregnancy test is positive, it must be confirmed by a serum pregnancy test. During the Safety Follow-up period, urine pregnancy tests will be performed every month during the first 6 months at each site visit. Urine pregnancy tests will continue to be performed on a monthly basis during the remainder of the Safety Follow-up period with patients performing the test at home (using kits provided by the site) during months where there is no site visit and at each site visit occurring approximately every 3 months. Patients will be instructed to contact the site immediately in case the result of the home pregnancy test is positive. In such cases, the patient must visit the site for a confirmatory serum pregnancy test.
- ^m Open-label treatment with pirfenidone will be started at this visit, if the patient requests continued treatment with pirfenidone.
- ⁿ Handheld spirometry will be conducted by the patient every day in a seated position.
- ^o To provide handling evaluations and quality assurance for the daily spirometer assessments, nursing visits to the patient's home (or at another suitable location) will occur at least three times during the trial, namely between Weeks 1 and 4, between Weeks 8 and 12, and between Weeks 16 and 20. Additional home nursing visits may be conducted according to the investigator's judgment.
- ^p 6-Minute Walk Distance (6MWD) is used to evaluate the functional capacity of patients with lung disease.
- ^q Questionnaires will be self-administered prior to the patient receiving any information on disease status and prior to the performance of non-PRO assessments. Refer to [Appendix 2](#) for copies of the questionnaires and a brief description.
- ^r Includes any medication (e.g., prescription drugs, over-the-counter drugs, vaccines, herbal or homeopathic remedies, nutritional supplements) used by a patient from the washout period until 28 days after the last dose of trial treatment.
- ^s After informed consent has been obtained but prior to initiation of trial treatment, only serious adverse events caused by a protocol-mandated intervention should be reported. After initiation of trial treatment, all adverse events will be reported until 28 days after the last dose of trial treatment. After this period, all deaths, regardless of cause, should be reported. In addition, the Sponsor should be notified if the investigator becomes aware of any serious adverse event that is believed to be related to prior trial treatment (see Section 5.6). The investigator should follow each adverse event until the event has resolved to baseline grade or better, the event is assessed as stable by the investigator, the patient is lost to follow-up, or the patient withdraws consent. Every effort should be made to follow all serious adverse events considered to be related to trial treatment or trial-related procedures until a final outcome can be reported.
- ^t Not applicable for a site that has not been granted approval for RBR sampling.
- ^u If a patient discontinues the trial between weeks 24 and 28, final assessments according to the Follow-up visit for week 28 should be performed.

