3. TRIAL DESIGN

3.1 DESCRIPTION OF THE TRIAL

This is a multicenter, international, double-blind, two-arm, randomized, placebo-controlled Phase II trial in patients with fibrosing ILD who cannot be classified with moderate or high confidence into any other category of fibrosing ILD by MDT review ("unclassifiable ILD"). Patients will be randomized in a 1:1 ratio, on a double-blind basis using a stratified algorithm, to receive either pirfenidone (801 mg TID) or placebo. The randomized patients will be stratified by concomitant MMF treatment (yes/no), the presence/absence of IPAF as defined by the MDT.

Most established MDTs have access to clinical, radiologic, and pathology expertise, and should have a sufficient case load of ILDs per year. Access to rheumatology expertise will be at the discretion of the MDT.

In total, approximately 90 clinical centers (sites) in Australia, Europe, the Middle East, and North America are expected to enroll approximately 250 patients. Patients who are withdrawn from the trial will not be replaced. The trial design is represented in [Figure 1](#).

After discussing the risks and benefits of the trial with the investigator and providing informed consent, patients will be required to taper and/or discontinue all prohibited medications (Section [4.4.2](#)) in the 28 days prior to the start of screening during the

washout period. If a prohibited medication must be tapered, the process must start early enough so that the patient discontinues the medication in the 28 days prior to the start of screening. After completing the washout period, patients will enter screening, which lasts up to 21 days. During screening, patients will be evaluated for eligibility based on the inclusion and exclusion criteria. Patients not taking a prohibited medication will forgo the washout period and directly enter screening.

At the end of screening, patients will be randomized (Day 1) to receive either pirfenidone or placebo (1:1 ratio).

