Following treatment initiation, the daily dosage will be titrated to the full dosage of nine capsules per day over a 14-day period as outlined in [Table 2](#) . After the titration period, trial treatment will continue through Week 24 and monitoring will be conducted by site visits. Patients should remain on a stable maintenance dose for the duration of the treatment period unless the dose is reduced or dosing is interrupted to manage an adverse event (see Section [5.1.1](#)). Any patient with an actual or anticipated interruption of trial treatment for a period of ≥ 28 consecutive days will be reported by telephone to Roche's medical monitor or designee to discuss the circumstances of the case. Once the patient restarts trial treatment, the dose must be re-titrated over 14 days as described in [Table 2](#) . A Follow-up Visit will occur 28 days after the end of the 24-week double-blind treatment period.

[figure not shown]
After completion of the double-blind treatment period and the Follow-up Visit at Week 28, the Sponsor will offer the possibility to the patients to receive open-label pirfenidone within the trial protocol in a safety follow-up period of up to 12 months. During the safety follow-up period, the patients should be evaluated by the investigator approximately every 3 months. A final Follow-up Visit will be performed at the end of the safety period, 28 days after the last open-label dose.

Table 2 Titration Schedule

Treatment Days	Dosage
Days 1 through 7	One capsule three times daily with meals
Days 8 through 14	Two capsules three times daily with meals
Day 15 onwards	Three capsules three times daily with meals

The Sponsor will provide trial treatment on a double-blind basis. The design that will be utilized in this trial is shown in [Figure 1](#) .

Figure 1 Trial Schema

¹ Patients will be required to taper and/or discontinue all prohibited medications in the 28 days prior to the start of screening during the washout period. Patients not taking a prohibited medication will forgo the washout period and directly enter screening.

² Informed consent must be documented before any trial-specific screening procedure is performed, and may be obtained either at the Washout or Screening Visits.

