4.3.4 Continued Access to Pirfenidone

After completion of the double-blind treatment period, the Sponsor will offer the possibility to the patients to receive continued access to pirfenidone in a safety follow-up period of up to 12 months, within this clinical trial protocol. A final Follow-up Visit will be performed at the end of the safety period, 28 days after the last open-label dose.

At the end of the 24-week double-blind treatment period, in order to maintain blinding, all patients will discontinue treatment over a 28-day period and return for the Follow-up Visit.

For patients who could benefit from participating in the 12-month safety follow-up period, according to the investigator's judgment, open-label pirfenidone will be started on the 28-day Follow-up Visit, using the titration schedule in [Table 2](#) . During the 12-month safety follow-up period, initially, patients will be evaluated at monthly visits for the first 6 months. At the end of the first 6 months, patients will be evaluated at each site visit occurring approximately every 3 months until the end of the safety follow-up period. In addition, at the end of the first 6 months, patients will perform home pregnancy tests at each month where there is no site visit. Patients will be provided with home pregnancy test kits and will be instructed to contact the site immediately should the test result be positive. In such cases, the patient must visit the site for a confirmatory serum pregnancy test. Refer to Schedule of Assessments for the assessments to be performed during this safety follow-up period ([Appendix 1](#)). The dose of pirfenidone used during the safety follow-up period is in accordance to section 4.3.2.1.

Following the end of the 12-month safety follow-up period, the Sponsor will offer post-trial access to the trial treatment (pirfenidone), free of charge, to eligible patients in accordance with the Roche Global Policy on Continued Access to IMP, as outlined below.

A patient will be eligible to receive Pirfenidone (Esbriet®) after completing the trial if all of the following conditions are met:

- The patient has a life-threatening or severe medical condition and requires continued trial treatment for his or her well-being
- There are no appropriate alternative treatments available to the patient
- The patient and his or her doctor comply with and satisfy any legal or regulatory requirements that apply to them.

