5.1.1.1 Hepatic Function

Elevations in ALT and AST $>3 \times$ ULN have been reported in patients receiving therapy with pirfenidone. Rarely, these have been associated with concomitant elevations in bilirubin. LFTs (ALT, AST, and bilirubin) should be conducted prior to the initiation of treatment with pirfenidone and subsequently at monthly intervals for the first 6 months. In the event of significant elevation of liver aminotransferases, the dose of pirfenidone should be adjusted or treatment discontinued according to the guidelines listed in [Table 3](#). See Sections 5.4.2.11 and 6.4.1 of the Investigator's Brochure for more details.

Patients with clinically significant hepatic impairment will be excluded from this trial (see Section 4.1.2).

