4.2.1 Study Days

Study days will be defined as the number of days since randomization, and is calculated as:

- Study day = Assessment date randomization date + 1, for assessments on or after the randomization date.
- Study day = Assessment date randomization date, for assessments before the randomization date.

The day of randomization will be study day 1.

Pirfenidone — F. Hoffmann-La Roche Ltd

4.2.2 Baseline and Screening Observations

Table 1 Definition of Baseline and Screening Observations

| | Definition |
|----------------|---|
| Baseline data | Baseline is defined as the last valid assessment prior to first intake of randomized study drug (pirfenidone/placebo). |
| | This may not be the same as the Day 1 (Week 1) visit as per eCRF. In case that Day 1 (Week 1) visit data is missing and the randomized treatment is given, data from the screening period will be used as baseline. In addition, if randomized treatment is not given then baseline will be defined as the last valid assessment collected either screening or day 1. |
| | Generally, it is assumed that measurements referring to the Day 1 (Week 1) visit have been performed before randomized study drug (pirfenidone/placebo) was given. |
| | Adverse events occurring on the date of first randomized pirfenidone/placebo treatment will not be considered baseline, but treatment-emergent. |
| Screening data | Screening measurements are all the measurements performed before the randomization date. |

4.2.3 On-treatment Assessments for Efficacy Analyses (Double-blind Treatment Period)

For efficacy analyses, on-treatment assessments will be the assessments performed on or after the randomization date until the double-blind treatment completion or discontinuation date.

4.2.4 On-treatment Assessments for Safety Analyses (Double-blind Treatment Period)

For safety analyses, on-treatment assessments will be the assessments performed on or after the first dose of randomized pirfenidone/placebo date until the last positive dose of randomized treatment plus 28 days.

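### Placebo completers take their first pirfenidone dose at the Week 28 Follow-up Visit with no liver test or pregnancy test scheduled there: a minor gap that is cheap to close

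*Protocol*

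**What the plan says.** Protocol Section 4.3.4 and footnote m of Appendix 1 agree on when open-label treatment starts for patients who finish the double-blind period. Section 4.3.4 says that "open-label pirfenidone will be started on the 28-day Follow-up Visit, using the titration schedule" is the route in, and footnote m says: "Open-label treatment with pirfenidone will be started at this visit, if the patient requests continued treatment with pirfenidone". Before that visit, "in order to maintain blinding, all patients will discontinue treatment over a 28-day period and return for the Follow-up Visit". Section 3.1 gives the interval: "A Follow-up Visit will occur 28 days after the end of the 24-week double-blind treatment period".

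In Appendix 1 the Week 28 column is marked for vital signs, ECG, trial treatment, concomitant medications and adverse events. The Chemistry and Pregnancy test cells are blank. SAP Appendix 2 has the same blanks, in both SAP versions supplied.

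Section 5.1.1.1 says liver function tests (LFTs) "should be conducted prior to the initiation of treatment with pirfenidone and subsequently at monthly intervals for the first 6 months". It gives no maximum age for the pre-treatment result. For the open-label period, footnote k states that "LFTs will be performed every month during the first 6 months", and footnote l sets monthly urine pregnancy tests. Neither names a test at the visit where dosing begins, and no day is given for the Month 1 visit.

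**The concern.** For a placebo patient who completes 24 weeks and then enters open label, Week 28 is the first exposure to a drug whose protocol lists ALT and AST elevation as a known risk and makes pregnancy a reason to stop. Any silent liver-test rise, or any pregnancy, that arises in the off-drug month would not be found by a scheduled test before that dose.

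The plan schedules more at its other two starting points. On Day 1 both tests are marked again, although "patients will enter screening, which lasts up to 21 days", so a screening result is already recent. At the Early Treatment Discontinuation Visit, where a placebo patient withdrawn after unblinding may start open label the same day (Section 4.2; Appendix 1, footnote b), both tests are also marked. Those marks may be meant as exit assessments, but the effect is that two groups of placebo patients start the same drug with different scheduled testing. ECG, by contrast, is marked at both Week 24 and Week 28.

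**Working it through.** **1. The plan's own interval.** Week 24 is 24 × 7 = Day 168 and Week 28 is 28 × 7 = Day 196. The difference is 196 − 168 = 28 days, as Section 3.1 states.

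**2. Marks in Appendix 1, by row.**

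| Row | Day 1 | Week 24 | Early Treatment Discontinuation | Week 28 | Open-label visits |
|---|---|---|---|---|---|
| Chemistry (includes LFTs) | yes | yes | yes | blank | LFTs only |
| Pregnancy test | yes | yes | yes | blank | yes |
| ECG | yes | yes | yes | yes | blank |
| Trial treatment | yes | blank | blank | starts (footnote m) | yes |

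**3. Age of the newest scheduled result at the first open-label dose.**
- Nominal: 28 days.
- With the ±5-day window on the Follow-up Visit only: 28 − 5 = 23 to 28 + 5 = 33 days.
- With both visit windows used independently: 191 − 173 = 18 to 201 − 163 = 38 days.

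At the randomized start, a screening result is at most 21 days old and a further sample is scheduled on the day itself.

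**4. Time to the next scheduled LFT.** Assume Month 1 falls 28 to 30 days after Week 28. The next LFT then comes 224 − 168 = 56 to 226 − 168 = 58 days after Week 24. The on-drug part (28 to 30 days) is close to the double-blind equivalent (Day 28 − Day 1 = 27 days), so the excess is the off-drug month only.

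**5. Patients concerned.** The ceiling is about 125 placebo patients. Open-label uptake is not given; assume 50% to 90%.
- Placebo: 125 × 0.5 ≈ 63 to 125 × 0.9 ≈ 113.
- Both arms: 250 × 0.5 = 125 to 250 × 0.9 = 225.

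**6. Expected undetected liver-test rises.** The documents give no rate; assume 0.1% to 1% per 28 days.
- Placebo: 63 × 0.001 = 0.06 to 113 × 0.01 = 1.13.
- Both arms, applying the same rate to the pirfenidone arm: 125 × 0.001 = 0.13 to 225 × 0.01 = 2.25.

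**7. Expected pregnancies.** Assume 2% to 10% of entrants are women of childbearing potential: 125 × 0.02 ≈ 3 to 225 × 0.10 ≈ 23. Using the protocol's contraceptive failure limit of under 1% per year as an upper bound:
- 3 × 0.01 × 28/365 = 0.002 to 23 × 0.01 × 28/365 = 0.018.

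**The case against.** The strongest reply is that nothing is breached. Section 5.1.1.1 asks for LFTs before pirfenidone and then monthly, and a Week 24 panel satisfies it. A 28-day-old result is no older than the spacing the protocol accepts on drug, and this interval is off drug. That stands. A reader might infer a violation of the hepatic monitoring rule, but the text does not support one.

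A reader might also set 28 days against zero, as if Day 1 had a reviewed pre-dose liver result. The documents do not go that far. Section 4.5.1 makes the completed screening evaluations the gate to enrollment, and no text requires the Day 1 chemistry to be reviewed before dosing. SAP 4.2.2, Table 1, does assume that "measurements referring to the Day 1 (Week 1) visit have been performed before randomized study drug (pirfenidone/placebo) was given", but this serves to define the analysis baseline. For a reviewed liver result the supported contrast is 28 days against at most 21. The same-day contrast is more convincing for the urine pregnancy test.

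Nor is Week 28 the first pirfenidone dose for every placebo patient. Those unblinded early may start at the Early Treatment Discontinuation Visit, where both tests are marked. The gap belongs to the Week 28 route.

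There are real safeguards:
- Dosing restarts by titration, at one capsule TID for the first week.
- Vital signs, adverse events and concomitant medications are scheduled at Week 28, and entry to open label depends on the investigator's judgment.
- Week 24 laboratory abnormalities judged clinically significant are adverse events and are followed until resolved or stable (Sections 5.3.5.4 and 5.5.1).
- A placebo completer already has eight scheduled LFTs: screening, Day 1, and Weeks 4, 8, 12, 16, 20 and 24.
- Contraception and immediate pregnancy reporting both extend to 58 days after the last dose.

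Footnotes k and l would let a site test at the start of the open-label period. With about 90 sites, though, practice could differ, because the Week 28 cells are blank. The safeguards reduce the size of the problem but do not schedule the missing tests.

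**Conclusion.** The point holds as a minor, inexpensive safety improvement. Placebo completers entering by the Week 28 route start pirfenidone at a visit with no scheduled LFT or pregnancy test, on results nominally 28 days old (18 to 38 at the extremes of both windows).

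The interval and the blank cells come directly from the documents. The yield does not: about 0.1 to 1.1 undetected liver-test rises among placebo entrants, and fewer than 0.02 pregnancies across both arms, rest on assumed uptake, event rates and share of women of childbearing potential. The pregnancy figure also assumes that contraception is used as required. The both-arm liver figure (up to about 2.3) probably overstates the pirfenidone arm, where a normal Week 24 value on drug is itself reassuring.

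A reader might go on to infer a defect in the SAP's open-label laboratory displays, or an effect on the trial's comparison. The documents support neither: SAP 4.7 is workable as written, and no efficacy or double-blind result is touched.

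**What to change.** In the Week 28 column of Appendix 1, mark the footnote-k LFTs (AST, ALT, bilirubin, alkaline phosphatase) and, for women of childbearing potential, a urine pregnancy test. Apply this to every patient entering open label, because treatment assignment is still blinded at that visit.

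- Read the urine test before the first open-label dose.
- Draw the LFT sample at the same visit, before dosing. Review it as soon as the local result is available, within the first titration week, when the dose is 3 × 267 = 801 mg/day, one third of the full 2403 mg/day. Apply Table 3 if it is abnormal.

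This keeps the start of dosing at the visit, as footnote m and Section 4.3.4 require, and avoids the extra attendance that a pre-visit draw would need. The price is that a liver result may arrive after the first doses.

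The cost is one additional local blood sample per entrant and one urine test per woman of childbearing potential, at an existing visit. No SAP change is needed: the visit windows in SAP 4.9 already cover laboratory data and include the Follow-up visit.
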